It is possible that EEG neurofeedback, which focuses on improving abnormal brainwave patterns, could provide certain therapeutic benefits to individuals with PPA or post-stroke aphasia, either by directly affecting neural networks that underlie language, or more generally by reducing anxiety and inattention through behavioral conditioning. Reduction of anxiety in neurological diseases can be beneficial not only for functional performance but also sleep duration and quality. We will couple EEG neurofeedback with Verb Network Strengthening (VNeST), a behavioral speech therapy program targeting verb naming skills, to examine if EEG neurofeedback can enhance gains made in traditional behavioral speech-language therapy, which is the current gold standard of care for aphasia treatment.

We hypothesize that EEG neurofeedback training will be more beneficial than sham training for improvement of communication, anxiety, and sleep quality. The primary aims of this proposed study are to (1) determine if EEG neurofeedback training coupled with behavioral speech-language therapy results in significantly greater communication skills, compared to sham EEG feedback training coupled with behavioral speech-language therapy in participants with PPA and post-stroke aphasia, and (2) determine if EEG neurofeedback training results in significantly reduced anxiety, better sleep quality and reduced use of sleep aids, compared to sham EEG feedback training in participants with PPA and post-stroke aphasia. This study also aims to investigate characteristics of participants most responsive to neurofeedback training and to examine whether or not neurofeedback improves functional connectivity in language and attention networks in patients with PPA and post-stroke aphasia.

2. Objectives (include all primary and secondary objectives)

Primary Objective:

The primary objective of this study is to determine whether 4-channel EEG neurofeedback training can augment traditional speech-language therapy and improve language and cognitive outcomes in individuals with PPA and post-stroke aphasia. A double-blind, sham controlled, within-subject crossover design with randomized order of treatment will be used, to allow each participant to serve as his or her own control. Participants will be randomly assigned to receive

Date: November 11, 2021
Principal Investigator: [name]
Application Number: IRB00242136
NCT# NCT04290988

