Study Title: Circuitry Assessment and Reinforcement Training Effects on Recovery (CARTER)

either an active EEG neurofeedback intervention period first followed by a sham intervention period, or a sham intervention period first followed by an active EEG neurofeedback intervention period. Participants will receive 15 training sessions within the active EEG neurofeedback intervention period and 15 sessions within the sham intervention period. Each participant will receive 2-5 sessions per week depending on their preference and availability. All participants will receive traditional behavioral speech-language therapy while simultaneously undergoing active or sham neurofeedback. Speech-language therapy will be performed within the same session as the active/sham neurofeedback training. The EEG neurofeedback and sham intervention periods will be separated by a 1 week “wash out period”. Communication will be evaluated before therapy and again in the week immediately following therapy, for each intervention period.

To evaluate the effects of EEG neurofeedback on communication skills in participants with post-stroke aphasia and PPA, we will carry out a randomized double-blind, sham controlled, within-subject crossover trial design. The Object Action Naming Battery (OANB) (Druks, 2000) will be used to evaluate communication skills by testing participants at baseline and in the week immediately following treatment. The primary outcome variable will be the change in number of Content Units (CU) in picture description, because this measure is a sensitive measure of communication impairment in both left and right hemisphere stroke (Agis et al., 2016) and PPA (Berube & Hillis, 2019). Secondary outcome variables will be change in accuracy of naming on the OANB, change in number of words produced on the Controlled Oral Word Association test (COWA, a measure of attention, executive function, and word-retrieval), change in quality of sleep measured with The Pittsburgh Sleep Quality Index (PSQI), change in anxiety measured with State Trait Anxiety Inventory, and change in frequency of use of sleep medications.

Hypothesis 1A. Participants will show greater improvement in correct CU in picture description from baseline to 1-week post treatment, during the EEG neurofeedback condition than during the sham condition.

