Hypothesis 1B. Participants will show greater improvement in accuracy of naming on the OANB from baseline to 1-week post treatment, during the EEG neurofeedback condition than during the sham condition.

Hypothesis 1C. Participants will show greater improvement in number of words produced on the COWA from baseline to 1-week post treatment, during the EEG neurofeedback condition than during the sham condition.

Hypothesis 1D. Participants will show greater improvement in sleep quality measured with the PSQI from baseline to 1-week post treatment, during the EEG neurofeedback condition than during the sham condition.

Hypothesis 1E. Participants will show greater improvement in state anxiety (S-anxiety on the State Trait Anxiety Inventory; STAI) from baseline to 1-week post treatment, during the EEG neurofeedback condition than during the sham condition.

Date: November 11, 2021
Principal Investigator: [name]
Application Number: IRB00242136
NCT# NCT04290988
Study Title: Circuitry Assessment and Reinforcement Training Effects on Recovery (CARTER)

Hypothesis 1F. Participants will show greater reduction in the frequency of use in medications used to improve sleep from baseline to 1-week post treatment, during the EEG neurofeedback condition than during the sham condition.

Secondary Objective: The secondary objective of this study is to examine which patient characteristics (stroke hemisphere, PPA variant, baseline severity of communication/sleep deficits or anxiety, baseline QEEG deficiencies) predict the best response to treatment. This will help improve the selection of specific treatments for individual patients in the future. This is an exploratory Aim, as we do not have any preliminary data or literature on which to base hypotheses about the characteristics that will predict change in the primary outcome measure. However, the literature does indicate that neurofeedback can reduce anxiety in stroke patients (Nan, et al. 2019), in people with major depression (Wang et al., 2019), and in people with post-traumatic stress disorder or generalized anxiety disorder (Banerjee & Argáez C, 2019). There is also preliminary evidence that neurofeedback may improve sleep in cancer patients (Hetkamp et al., 2019). Reduction of anxiety with or without improved sleep may be one mechanism of the potential effect of neurofeedback on communication.

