The primary outcome variable will be the change in number of Content Units (CU) in picture description from baseline to 1-week post-treatment. Hypothesis 1A is: Participants will show greater improvement in CU from baseline to 1-week post treatment, during the EEG neurofeedback condition than during the sham condition.

To test Hypothesis 1A, we will subtract baseline CU from 1-week post-treatment CU, for each condition. We will use a paired t-test to determine if, as a group, patients showed greater increase in CU during the neurofeedback condition compared to the sham condition. We will also carry out paired t-tests for post-stroke aphasia and PPA separately, to determine if the effect was greater in one group.

b. Secondary outcome variables

Hypothesis 1B-F take the form of: Participants will show greater improvement in [outcome variable] from baseline to 1-week post treatment, during the EEG neurofeedback condition than during the sham condition.

To test each hypothesis 1B-F, we will subtract baseline score from follow up scores (1-week post-treatment), for each condition. We will use paired t-tests to determine if, as a group, patients showed greater improvement during the neurofeedback condition compared to the sham condition, at each follow-up. We will correct for multiple comparisons using a Bonferroni correction.

Hypothesis 2A is: We will be able to identify baseline characteristics (demographics and baseline severity measures, as well as qEEG abnormalities) that influence change in the primary outcome measure (change in CU in picture description from baseline to 1-week post-treatment).

To test this hypothesis, we will carry out multivariable linear regression, with the dependent variable (change in CU in picture description from baseline to 1-week post-treatment), and independent variables of age, baseline CU, baseline OANB, baseline COWA, baseline sleep quality, baseline S-anxiety (STAI), brainwave activity (absolute power, peak amplitude frequency) in each frequency band (alpha, beta, theta, delta, gamma) on qEEG.

Hypothesis 2B is: We will be able to identify changes in secondary outcome measures and changes in qEEG that correlate with the primary outcome measure (change in CU from baseline to 1-week post-treatment). These results will allow us to identify variables to explore the mechanisms of the effects.

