To test this hypothesis, we will carry out Pearson correlations between the dependent variable (change in CU in picture description from baseline to 1-week post-treatment), and change in CU, change in OANB, change in COWA, change in absolute power and peak amplitude frequency within each frequency band (alpha, beta, theta, delta, gamma) on qEEG, change in coherence on qEEG (e.g., coherence between left and right hemispheres).

Hypothesis 3A is: Greater improvement in qEEG normalization toward healthy control group (e.g. alpha enhancement with absolute power and peak amplitude frequency ≤ 1.5 standard deviations away from healthy group average) will be observed in the EEG neurofeedback training condition compared to sham training condition.

Date: November 11, 2021
Principal Investigator: [name]
Application Number: IRB00242136
NCT# NCT04290988
Study Title: Circuitry Assessment and Reinforcement Training Effects on Recovery (CARTER)

To test this hypothesis, we will compare baseline and follow-up z-scores for absolute power and peak amplitude frequency of each of the frequency bands (alpha, beta, theta, delta, gamma) by subtracting the absolute value baseline z-score from the absolute value follow-up z-scores for each condition. We will use paired t-tests to determine if, as a group, patients showed greater improvement during the neurofeedback condition compared to the sham condition, at each follow-up. We will correct for multiple comparisons using a Bonferroni correction. We will also carry out paired t-tests for post-stroke aphasia and PPA separately, to determine if the effect was greater in one group.

Hypothesis 3B is: Greater connectivity within the attentional network and the language network (and right hemisphere homologues) will be observed in the EEG neurofeedback training condition compared to sham training condition.

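### The exploratory 2A regression states no active-versus-sham contrast and omits stroke hemisphere and PPA variant; the 2B correlations leave out anxiety, sleep quality and sleep-medication change

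*Combined protocol and SAP*

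**What the plan says.** The aims paragraph just before Section 2 states: "This study also aims to investigate characteristics of participants most responsive to neurofeedback training". The Secondary Objective in Section 2 asks "which patient characteristics (stroke hemisphere, PPA variant, baseline severity of communication/sleep deficits or anxiety, baseline QEEG deficiencies) predict the best response to treatment", calls the aim exploratory, and adds: "This will help improve the selection of specific treatments for individual patients in the future".

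Section 7b tests Hypothesis 2A as follows: "we will carry out multivariable linear regression, with the dependent variable (change in CU in picture description from baseline to 1-week post-treatment"). The listed predictors are age; baseline CU, OANB, COWA, sleep quality and state anxiety; and two qEEG measures in each of five frequency bands.

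Hypothesis 2B concerns changes in secondary outcomes and in qEEG that correlate with CU change. The Primary Objective text defines five secondary outcomes: OANB, COWA, PSQI, STAI and sleep-medication use. The 2B test in Section 7b correlates "change in CU in picture description from baseline to 1-week post-treatment), and change in CU, change in OANB, change in COWA", followed by qEEG power, peak frequency and coherence.

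Two features of the design matter here: "All participants will receive traditional behavioral speech-language therapy while simultaneously undergoing active or sham neurofeedback", and "Communication will be evaluated before therapy and again in the week immediately following therapy, for each intervention period".

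**The concern.** CU change in one period mixes any neurofeedback effect with gain from speech-language therapy, practice and disease course. A characteristic that predicts only the general part would look the same in the 2A regression as one that predicts response to neurofeedback. The objective is meant to guide treatment selection, and Section 7c uses the study to prepare a multicenter trial, so the two should not be confused.

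For 2B, the Secondary Objective says: "Reduction of anxiety with or without improved sleep may be one mechanism of the potential effect of neurofeedback on communication". Section 7b says 2B is to help explore mechanisms. The anxiety and sleep changes that would bear on this are the ones missing from the list.

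**Working it through.** **Comparing the texts**

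- *Contrast.* Hypotheses 1A, 1B-F, 3A and 3B in Section 7 each state neurofeedback against sham. 2A does not, and 2B names no condition either.
- *2A predictors.* 6 clinical terms + 2 qEEG measures × 5 bands = 16. None is condition, hemisphere or PPA variant. The separate stroke and PPA t-tests in Section 7a cover diagnosis only. 2A does not say which period's baseline supplies its predictors.
- *2B outcomes.* OANB and COWA are listed (2 of 5). STAI, PSQI and sleep-medication use are not. CU change is listed against itself, probably a drafting slip.

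**Sample size.** The plan's target reproduces: 8 per year × 5 years × 2 groups = 80.

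**Assumptions.** The documents give no CU reliability, correlations or alpha. Assumed: n = 80 without attrition, 40 per sequence, two-sided 0.05, CU reliability 0.7-0.9, independent measurement error at each visit, and target correlation 0.3.

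**2A, general predictor** (same correlation with CU change in both periods, no link to neurofeedback)

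- Raw active-period change, 16 terms, residual df = 80 − 16 − 1 = 63: t ≈ 0.3/√(1 − 0.09) × √63 = 0.3145 × 7.94 = 2.50. The critical value is 2.00, so it is flagged in about Φ(0.50) = 69%.
- Simulation gives 69-71% with Visit 1 baseline CU and 76-87% with each period's own baseline.
- In the active-minus-sham difference the general gain cancels, and the rate is about 5%.
- At correlations of 0.2 and 0.4, the raw rates over both baseline choices are 35-53% and 93-99%. The difference stays at 4-6%.
- With n = 40 the raw rate at 0.3 is only about 31%.

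**2A, true modifier** (correlated 0.3 with active-period change only)

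Write the error variance at each visit as 1 − r. Raw change has variance 2(1 − r). If Visit 18 is both the first follow-up and the second baseline, the difference is ±(2·V18 − V1 − V34), with variance 6(1 − r). With a separate second baseline it is 4(1 − r). The SD ratios are √3 = 1.73 and √2 = 1.41.

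Adding sequence, sequence × baseline CU, diagnosis, hemisphere and two variant terms (three variants assumed) gives 22 terms and 57 residual df.

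| Analysis | Approximate t | Hand power | Simulated |
|---|---|---|---|
| Raw active change | 0.3145 × √63 = 2.50 | 69% | about 70% |
| Difference, Visit 18 shared | 0.3145/1.73 × √57 = 1.37 | 26% | 27-29% |
| Difference, separate baseline | 0.3145/1.41 × √57 = 1.68 | 37% | 38-41% |

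**2B**

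- A stable general gain giving a correlation of 0.3 between the two changes: atanh(0.3) × √77 = 2.72, and Φ(2.72 − 1.96) = 78% flagged. After differencing it is 5%, provided errors are independent between outcomes.
- If errors at the same visit correlate c across outcomes, any contrast using the same visit weights also has correlation c, so differencing does not help. With no gain and no effect, c = 0.1, 0.2 and 0.3 give Φ(0.88 − 1.96) = 14%, Φ(1.78 − 1.96) = 43% and 78%. Simulated rates after differencing run from 14% to 79%.

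**The case against.** Hypothesis 2A as worded asks what influences change in CU, and the regression answers that question. The Secondary Objective speaks of response to treatment; only the aims paragraph speaks of response to neurofeedback. Section 2 says that 2B will point to variables to explore as interactions, which suggests a screening step. Section 7a computes CU change for each condition, so fitting 2A by condition is not excluded. This stands in part: the plan is inconsistent with itself rather than plainly wrong. But no interaction model is specified anywhere, so the aims-paragraph question has no stated analysis.

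Two further objections stand. The documents give no left/right split of strokes, so a hemisphere term may be nearly inestimable. And differencing in 2B removes a stable general gain but not error shared within a visit.

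A reader might infer that the trial's main comparison is compromised, or that anxiety and sleep go unanalysed. The documents support neither: 1A is a paired active-versus-sham test, and 1D-1F compare sleep quality, anxiety and sleep medication by condition. A reader might also infer that a differenced 2B correlation would show mechanism. The shared-error calculation shows that it would not.

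**Conclusion.** The point holds for the exploratory aims. As written, 2A cannot separate predictors of response to neurofeedback from predictors of general change. It leaves out two characteristics that the objective names, and 2B omits three of five secondary outcomes, including those tied to the proposed mechanism. These textual findings need no assumption.

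The size does. About 70% against 5% for a general predictor rests on a correlation of 0.3, 80 completers and CU reliability of 0.7-0.9. The raw rate falls with fewer patients, and Section 7c only hopes to reach 80. The 2B improvement from 78% to 5% also needs errors that are independent between outcomes. The change is worth making before analysis; the primary test does not depend on it.

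**What to change.** 1. **2A.** Make the dependent variable each patient's active-period CU change minus sham-period CU change, or test condition-by-predictor terms in a mixed model. Take predictors from Visits 1-2. Include sequence coded +0.5/−0.5 and its interaction with centred baseline CU. The coding matters: with no effect present, baseline CU is flagged in 4-6% of simulated analyses with it, but in 8-23% with 0/1 coding. If the raw-change regression is kept, label it *predictors of CU change*.
2. **Missing characteristics.** Add diagnosis, PPA variant within PPA, and stroke hemisphere within stroke if both sides are adequately represented; otherwise describe hemisphere only. The full 22 terms leave 80/22 = 3.6 patients per term, so any reduction or penalisation should be prespecified by the sponsor's statistician.
3. **2B.** Replace the CU-change entry in the list with change in STAI state anxiety, PSQI and sleep-medication use, and correlate active-minus-sham differences. Report exploratory associations with confidence intervals, not evidence of mechanism, because shared visit-level error remains.

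**Cost.** SAP wording, hemisphere and variant from the diagnostic record, and lower power. The SD ratios of 1.73 and 1.41 are upper figures: if a stable gain correlates 0.5 with each period's change, raw variance becomes 2(1 − r)/0.75 and they fall to 1.50 and 1.22. A null 2A result would not rule out a moderate modifier, and the report should say so.

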To test this hypothesis, we will compare baseline and follow-up z-scores for coherence in each of the frequency bands (alpha, beta, theta, delta, gamma) by subtracting the absolute value baseline z-score from the absolute value follow-up z-scores for coherence in each condition. We will use paired t-tests to determine if, as a group, patients showed greater improvement during the neurofeedback condition compared to the sham condition, at each follow-up. We will correct for multiple comparisons using a Bonferroni correction. We will also carry out paired t-tests for post-stroke aphasia and PPA separately, to determine if the effect was greater in one group.

c. Statistical plan including sample size justification and interim data analysis

Statistical Analyses

Statistical tests to evaluate each hypothesis are described above. No interim data analyses are planned, although we will become unmasked to condition after each participant completes the 5 week follow-up

Sample Size Determination

This study is a novel application of neurofeedback for treatment of aphasia, and we have no preliminary data to guide a power analysis. However, we will use this preliminary cross-over study (with each patient as their own control) to identify effect size (if any), in order to plan a randomized, double-blind, parallel, sham-controlled trial. For this preliminary trial, we plan to study 8 patients per year with post-stroke aphasia, and 8 patients per year with PPA, based on our other ongoing trials of post-stroke aphasia and PPA, in which we have found that it is feasible to recruit and retain 8-10 of each per year. We hope to obtain a total of 40 patients with post-stroke aphasia and 40 with PPA over 5 years, to obtain preliminary data for a multicenter, randomized, double-blind, parallel, sham-controlled trial, if the preliminary results are positive.

Missing Data

We plan to minimize missing data by avoiding prolonged intervals between conditions. Most of the study will take place within 7-11 weeks, with each person scheduled to have a 5 week follow up to determine if any changes are long-lasting. To minimize biases, analyses will be by

Date: November 11, 2021
Principal Investigator: [name]
Application Number: IRB00242136
NCT# NCT04290988
Study Title: Circuitry Assessment and Reinforcement Training Effects on Recovery (CARTER)

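### Hypothesis 2A regresses change in CU on the baseline CU subtracted to form it, with no sham contrast, so the baseline severity slopes are biased as predictors of response

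*Combined protocol and SAP*

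**What the plan says.** Section 7a defines the change score for Hypothesis 1A: "we will subtract baseline CU from 1-week post-treatment CU, for each condition". Section 7b then specifies a multivariable linear regression for Hypothesis 2A, "with the dependent variable (change in CU in picture description from baseline to 1-week post-treatment), and independent variables of age, baseline CU, baseline OANB", followed by "baseline COWA, baseline sleep quality, baseline S-anxiety (STAI), brainwave activity (absolute power, peak amplitude frequency) in each frequency band". No condition, order, period or diagnosis term is listed.

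The coefficients are meant to be interpreted. Hypothesis 2A reads: "We will be able to identify baseline characteristics (demographics and baseline severity measures, as well as qEEG abnormalities) that influence change". The Secondary Objective in section 2 says the aim is to find which characteristics "predict the best response to treatment. This will help improve the selection of specific treatments for individual patients in the future". It also states: "This is an exploratory Aim, as we do not have any preliminary data or literature" on which to base hypotheses about predictors.

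Two things are left open. The protocol gives no reliability for CU and mentions neither measurement error nor regression to the mean. It also does not say which baseline 2A uses. Section 2 has communication evaluated before and after each intervention period, and section 4a calls Visit 1 the baseline for the first period. Visit 18 is the only listed assessment between the two periods.

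**The concern.** A participant who happens to score low at baseline will tend to score nearer their usual level next time. That shows up as a gain, and the same low score is the predictor. Baseline severity can therefore look like a predictor of response when it predicts nothing.

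OANB and COWA are not subtracted into the outcome, but they carry information about true language ability. Once an error-prone baseline CU is in the model, they help to locate the true CU, and so can pick up positive slopes.

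The wider gap is that 2A models raw change. Speech therapy is given in both conditions, so raw change mixes any neurofeedback response with speech therapy, practice and regression to the mean. At stake is the secondary objective: an artefact could be carried forward as a guide to which patients to treat.

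**Working it through.** **Inputs from the protocol**
- Sample size (section 7c): "We hope to obtain a total of 40 patients with post-stroke aphasia and 40 with PPA over 5 years". This reproduces from the stated accrual: 8 per year × 5 years = 40 per diagnosis, and 40 + 40 = 80. It rests on feasibility, with no power calculation.
- Predictors (section 7b): age, baseline CU, OANB, COWA, sleep quality and S-anxiety make 6. Two qEEG measures × 5 bands make 10. Total 16, if there is one value per band.

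**Assumptions, none given in the protocol**
- CU reliability R from 0.7 to 0.95.
- OANB and COWA each correlate 0.6 with true CU and are otherwise independent of each other.
- The other predictors are unrelated to CU, and the data are normal.
- Individual true change is unrelated to baseline, with SD between 0 and 0.5 of the true-CU SD.

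**Step 1: baseline CU as the only predictor.** Write observed CU = T + e. Change contains −e and the predictor contains +e, so the slope is −var(e)/(var(T) + var(e)) = −(1 − R). At R = 0.9, 0.8 and 0.7 this is −0.10, −0.20 and −0.30.

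**Step 2: with OANB and COWA in the model.** Set var(T) = 1, so var(e) = (1 − R)/R. The two tests explain 2 × 0.36/1.36 = 0.529 of var(T), leaving 0.471. The baseline CU slope is then −var(e)/(0.471 + var(e)):
- R = 0.9: −0.111/0.582 = −0.19
- R = 0.8: −0.250/0.721 = −0.35
- R = 0.7: −0.429/0.899 = −0.48

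OANB and COWA each take a positive slope equal to the size of the CU slope × 0.6/1.36. At R = 0.8 that is 0.35 × 0.441 = 0.15.

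**Step 3: how often this reaches significance.** Simulated trials used n = 80, ordinary least squares with 16 predictors, and a two-sided 5% test. The table shows the false-positive rate for baseline CU; each range spans the assumed SD of true change.

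| CU reliability | Regressor is the baseline that was subtracted | Visit 1 CU is the regressor; each change uses its own period baseline |
|---|---|---|
| 0.95 | 14–44% | 7–14% |
| 0.9 | 33–73% | 13–23% |
| 0.8 | 72–95% | 27–40% |
| 0.7 | 92–99% | 40–50% |

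In the last column about half the participants in either condition change from Visit 18, whose error is not in Visit 1 CU. The slopes in step 2 are therefore roughly halved.

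Over all these settings OANB and COWA are each falsely significant in about 5–45% of trials. If they are uncorrelated with true CU, they stay at about 5%, and baseline CU, used as the subtracted baseline, is still falsely significant in 52–65% of trials at R = 0.8 (SD of change 0.3 to 0.5 of the baseline SD).

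**Step 4: a remedy that does not work.** Using post-treatment CU as the outcome while keeping baseline CU as a predictor raises the baseline CU slope by exactly 1 and leaves every other coefficient unchanged. The bias remains.

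**Step 5: a remedy that does.** Take the active-minus-sham difference in 1-week post-treatment CU (Visits 18 and 34), with Visit 1 CU as the baseline predictor. Visit 1 error is then absent from the outcome and true CU cancels. With order as a covariate, the false-positive rate for CU, OANB and COWA is about 4–6% in every setting, given no carryover.

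**The case against.** Several points on the other side stand.

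- **The size depends on things the protocol does not state.** At high reliability, with varied true change and Visit 1 CU as the regressor, the false-positive rate is only modestly above 5%. Assuming that no participant truly changes gives the top of each range. That is unrealistic in a population with progressive disease and 15 speech-therapy sessions in each period.
- **Baseline CU is a legitimate covariate.** Used only for adjustment, it is ordinary analysis of covariance. The fault lies in reading its coefficient as a predictor of response.
- **The aim is exploratory.** The trial is meant to supply preliminary data for a later one.
- **The remedy has its own assumption.** Visit 34 follows 30 speech-therapy sessions and Visit 18 follows 15, with a 1-week washout between periods. An order term absorbs average period and carryover differences, but not carryover that varies with severity.

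A reader might infer that the analysis is bound to report low baseline CU, together with relatively good naming and fluency, as the profile that responds best. The protocol does not support that. The direction of the bias is certain for any reliability below 1, but a significant result is not, and in most simulated trials OANB and COWA are not significant. Nor does the protocol say that 2A will decide who is treated, only that it should help future selection.

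**Conclusion.** The point holds as a bias in the interpretation of Hypothesis 2A. The baseline CU slope is pulled downward whenever CU is measured with error, and nothing in the protocol corrects for it. The 2A model cannot separate response to neurofeedback from regression to the mean, practice or speech therapy.

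The false-positive rate for baseline CU runs from about 7% to 99%. Where it falls depends mainly on CU reliability, on which baseline is the regressor, and on how much true change varies; all three are assumptions here. The effect on OANB and COWA is indirect and needs them to correlate with true CU.

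It would be wrong to infer that the trial's main result is compromised: the Hypothesis 1A test compares the two conditions and does not use this regression. The consequence is confined to the secondary objective. It should still be corrected, because that objective is meant to inform treatment selection.

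**What to change.** In section 7b, redefine the 2A outcome as the within-participant active-minus-sham difference in 1-week post-treatment CU (Visit 18 versus Visit 34). Take the baseline predictors from before the first period (Visits 1 and 2) and include treatment order as a covariate. State the assumption that carryover is unrelated to baseline severity.

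If the change-score model is also shown, say which baseline it uses and keep baseline CU as an adjustment covariate only. State that its coefficient, and those of baseline OANB and COWA, are not interpreted as predictors of response to neurofeedback.

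The core change is one sentence and needs no new data or participants. The real cost is that 2A moves from change within a condition to a difference between conditions. That is the quantity that response to neurofeedback requires.
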